The PI at each site is responsible for retaining all essential documents listed in the International Conference on Harmonization (ICH)/ Good Clinical Practice (GCP) Guidelines. All essential documentation for all study subjects are to be maintained by the investigator in a secure storage facility according to each military treatment facility's requirement. These records are also to be maintained in compliance with IRB, state, and federal medical records retention requirements, whichever is longest. All stored records are to be kept confidential to the extent provided by federal, state, and local law.

DCC

Access to study files at DCC (eCRFs) is restricted to staff members given specific study related tasks to perform. The files are maintained on controlled-access servers in accordance with DCC standard procedures.

10.3 At any point in the study, will you request, use, or access data from a DoD Database or the Military Health System (MHS)?

• Yes • No

10.4 Review the definitions below and respond to the following two questions. If you are not sure of the answers, email [contact] for assistance. The *Military Health System (MHS)* is defined as all DoD health plans and DoD health care providers that are organized under the

management authority of, or in the case of covered individual providers, assigned to o the Defense Health Agency (DHA), the Army, the Navy, or the Air Force MHS workfor are employees, volunteers, trainees, and other persons whose conduct, in the perform for the MHS, is under the direct control of the MHS, whether or not they are paid by th business associates are persons or entities that provide a service to the MHS and requ health information (PHI) to provide the service.	rce members nance of work ne MHS. MHS
Are you an MHS workforce member?	
 Yes, I am an MHS workforce member No, I am not an MHS workforce member 	
Are you an MHS business associate?	
 Yes, I am an MHS business associate No, I am not an MHS business associate 	
10.5 Have you consulted with an MHS data expert to determine the data elements required	for your study?
Consulting with a data expert often saves time later in the compliance process because the data expert can advise on the data available in the numerous MHS information systems, the quality of that data and the methods for encrypting and collapsing data. To schedule a consult with an MHS data expert, send an email to: ([contact]) • Yes, then complete the questions below according to the data consult • No, then complete the questions below according to the best of your knowledge	
10.6 Indicate how you will request data from the MHS. Select all that apply.	
 Talking with MHS health care providers or MHS health plans about specific research participants Obtaining MHS hard copy records specific to research participants Obtaining data from an MHS information system(s) 	
10.7 If you are obtaining data from an MHS information system(s), indicate whether you p data extract or whether you plan to access an MHS information system directly to creat	
A data extract is when the MHS or a contractor provides the data set directly to the researcher. When receiving a data set through data extract, the researcher may indicate whether the data elements should be provided as is, encrypted or collapsed. In contrast to a data extract, access to an information system means that the researcher may directly access an MHS information system and create a data set for the research study I Data Extract Access	
10.8 Do you intend to use only de-identified data from the MHS in your research study?	
There are different two methods for de-identifying data pursuant to HIPAA: 1) Safe Harbor Method: Removing all of the identifiers listed in Table 1 below, provided that the researcher does not have actual knowledge that the remaining data can be used alone or in combination with other information to identify the individual who is the subject of the information 2) Statistical Method: An expert, with appropriate knowledge of and experience with generally accepted statistical and scientific principles and methods for rendering information not individually identifiable, determines that the data is not individually identifiable O Yes O No	
10.9 Indicate the MHS information system(s) from which you will seek to obtain data	

If you do not know which system(s) contains the data elements you need, refer to the Guide for DoD Researchers on Using MHS Data or request guidance from an MHS data expert at: **DHA**. **[contact]**.

Below is a list of commonly used MHS systems. If the system from which you seek to obtain data is not listed below, list the name of the system in the "Other MHS Systems" category below **PHI Systems:**

MHS Information System	Requesting Data
: AHLTA	: Yes
: CHCS	: Yes
: ESSENTRIS	: Yes
: MDR	: Yes
PII-Only Systems:	
MHS Information System	Requesting Data
MHS Genesis	
	: Yes
Information System	: Yes Requesting Data

10.10 Do you intend to merge or otherwise associate the requested data with data from any sources outside of the MHS, including other DoD systems that are not part of the MHS?

- Yes, will merge data
- O No, will not merge data

10.11 Indicate the data elements about research participants or relatives, employers, or household members of the research participants that you will request from MHS hard copies or from MHS information systems. If you answered "yes" to question 10.9 above, also indicate non-MHS data elements about research participants or relatives, employers, or household members of the research participants that you will have access to in any form or medium.

Data Element(s)	MHS	Non-MHS Systems	MHS Hard Copies
1. Names			
2. Postal address with only town, city, state and zip code		V	
3. Postal address with all geographic subdivisions smaller than a state, including street address, city, county, precinct,			

zip code and their equivalent geocodes, except for the initial three digits of a zip code if, according to the current publicly available data from the Bureau of Census: 1) the geographic unit formed by combining all zip codes with the same three initial digits contains more than 20,000 people; and 2) the initial three digits of a zip code for all such geographic units containing 20,000 or fewer people is changed to 000		
4. Dates including all elements (except year) directly related to an individual, including birth date, admission date, discharge date, and date of death		
5. Ages over 89 and all elements of dates (including year) indicative of such age, unless you will only request a single category of "age 90 or older"		
6. Telephone numbers	V	
7. Fax numbers		
8. Electronic mail addresses	V	
9. Social Security numbers (SSNs)		
10. Medical record numbers		

	-	
11. Health plan beneficiary numbers		
12. Account numbers		
13. Certificate /license numbers		
14. Vehicle identifiers and serial numbers, including license plate numbers		
15. Device identifiers and serial numbers		
16. Web Universal Resource Locators (URLs)		
17. Internet Protocol (IP) address numbers		
18. Biometric identifiers, including finger and voice prints		
19. Full-face photographic images and any comparable images		
20. Any other unique identifying number, characteristic, or code (DEERs ID, EDIPN, Rank)		

If you are obtaining SSNs, provide a justification as to why and explain why a substitute cannot be used

Participants receiving >\$600 in compensation in one calendar year must fill out a W9 in order to receive a 1099 at the end of the year for IRS tax reporting purposes. Social security numbers are collected for this reason alone.

10.12 Do you believe it is possible for the MHS data to become identifiable because of triangulation, a small cell size, or any unique data element(s)?

Triangulation means using different data elements that are not themselves identifiable but that when combined can be used to identify an individual. For example, triangulation would use rank and race together to determine the identity of an individual with a particular health condition.

Small cell size means that there is only a small number of eligible individuals that satisfy the category description. Guidance for acceptable cell size is available from the Centers for Medicare and Medicaid Services. For example, the rank category of four star generals with a particular diagnosis may be less than 30, so the rank category may need to be expanded to include lower ranks.

A unique data element includes any unique features that are not explicitly enumerated in the categories of data in rows 1 - 20 of the table above (in Section 10.10), but that could be used to identify an individual. Unique data elements include characteristics that are not themselves identifying, such as the rank of general or admiral, or a race or gender, but within the context of other information could be identifiable.

Yes, I believe there is a reasonable possibility the MHS data will become identifiable
 No, I believe there is no reasonable possibility the MHS data will become identifiable

10.13 HIPAA Privacy Rule and Use of Protected Health Information in Research:

- N/A will not use or disclose protected health information (PHI)
- O HIPAA Authorization will be obtained
- O Use of a limited data set where a data use agreement will be obtained
- Waiver/alteration of HIPAA Authorization is being requested

10.14 Managing Data (Data Management and/or Sharing Plan) and/or Human Biological Specimens for this Study:

Include in this section the plan for acquiring data (both electronic and hard copy), access during the study, data/specimen storage and length of time stored, shipment/transmission, and the plan for storage and final disposition at the conclusion of the study. Describe any data agreements in place for accessing data within and/or outside of your institution (e.g., Data Sharing Agreement, Data Use Agreement, Business Agreements, etc.)

The only electronic links between the subject's name, DoD ID, SSN, and Study ID number will be on tracking spreadsheets at the clinical sites used for collecting information on ILI cases, as needed, from electronic medical records and will only be accessed by authorized study staff. During the study, source documents will be held in a secure cabinet with restricted access. Team members with access to the documents are counseled on the importance of maintaining the confidentiality of subjects' medical records and trained on human subjects' protection and HIPAA. All staff involved in this study have completed the required human subjects' protection and ethics training. In all electronic records used for data analysis, the subjects are not referenced by name, but only Study ID number. This method is designed to protect study subjects' medical information. All measures are put in place to protect the privacy of all subjects. The study will utilize passwords and firewalls to maintain confidentiality of data accessed via computer. The summary report generated from the interviews and completed questionnaires will not contain any subject identifying information.

To determine whether an individual has been enrolled previously at another study site, study staff at all sites will have the ability to query IDCRP data management systems to locate an individual. The data management systems are secure and can only be accessed by authorized individuals using a unique user ID/password combination.

The REDCap data entry system includes a server accessible by standard web browsers and devicebased applications. The server is hosted, maintained, and kept secure by the Henry M Jackson Foundation IT department. REDCap data is encrypted using 64-bit DES technology, and the REDCap server is configured to accept HTTPS connections only.

Tablets will be configured as follows:

- · The internal hard drive or folders containing study data will be encrypted
- Username/password will be required to log on to the tablet

• Study data transmission will employ a secure transmission protocol, (i.e SSL)

Email and cell phone number collection:

- Subject e-mails and cell phone numbers will be collected in REDCap accessed on a tablet using a secure wireless connection or on a computer using a secure landline connection, to the Infectious Disease Clinical Research Program Data Coordination Center. Emails and cell phone numbers may also collected on paper source documents and transcribed into tablets.
- Study data will be stored on the tablet hard drive only when the tablet is in offline mode; both the hard drive and the data folders are encrypted
- The tablet will periodically be uplinked via a secure connection at which time the study data will be transferred securely to the central study database

FluPRO daily symptom questionnaire:

- No personally identifying information will be collected in the questionnaire
- FluPRO daily symptom questionnaire information will be entered into a REDCap form via a URL provided by the DCC directly to the subject; the URL will be unique to the specific subject and questionnaire.

Salivary Sample Analysis will be performed at Johns Hopkins University (JHU). JHU will receive only coded samples and data, labeled by study ID.

10.15 Managing Data (Data Management and/or Sharing Plan) and/or Human Biological Specimens for Future Research:

If the study involves collecting, storing, or banking human specimens, data, or documents (either by the Investigator or through an established repository) for FUTURE research, address. How the specimens/data will be used, where and how data/specimens will be stored (including shipping procedures, storage plan, etc.), whether and how consent will be obtained, procedures that will fulfill subjects' request as stated in the consent, whether subjects may withdraw their data/specimens from storage, whether and how subjects may be recontacted for future research and given the option to decline, whether there will be genetic testing on the specimens, who will have access to the data/specimens, and the linkage, the length of time that data/specimens will be stored and conditions under which data/specimens will be destroyed.

Research use of data collected through this protocol will be coded and will not contain identifiers. Any DHA-derived PHI will be de-identified. Access to these data will be highly limited. Much of the subsequent research using the materials collected under the auspices of this study will be accomplishable through approved exempt or non-human use sub-studies. All research using the materials collected under this protocol will be conducted in accordance with an IRB-reviewed protocol. Data and tissue samples released for research use will be labeled by Subject ID only; data will be shared without any identifiers or links to individuals. The DCC will not share identifying information with investigators without explicit IRB approval.

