Subjects will undergo surveillance for influenza-like illness (ILI) during the influenza season, beginning 4 weeks post-vaccination and ending when nationwide influezna activity has returned to baseline (typically at the end of May). During this period, automated weekly email or text messages will be sent to subjects asking them if they have experienced ILI symptoms in the past 7 days. Subjects who meet the ILI case definition will be asked to complete an online 7-day symptom severity questionnaire and to schedule an ILI acute and convalescent virtual visit with a study coordinator, ascertain a self-collected nasal swab and self-collected blood samples. At the acute ILI virtual visit study coordinators will record subjects ILI history, hospitalization status, and work absences. The convalescent virtual ILI visit will take place approximately 28 days after answering "yes" to the surveillance survey (trigger"). Information on hospitalization status, and work absences will be updated at this visit.

Subjects will be monitored through as many ILI episodes as they experience, though subjects will only be compensated for the first 3 episodes. ILI episodes must be separated by at least 30 days. Information on ILI health care utilization and cost for data will be abstracted from the Military Health System Data Repository (MDR) database by IDCRP study staff at the end of each influenza season.

Up to 18,000 eligible subjects (or 6,000 subjects distributed evenly between the 3 study arms) will be block randomized in 1:1:1 (cell-culture-based vaccine, the recombinant vaccine, or the egg-based vaccine).

The study will compare the effectiveness of three types of FDA-licensed influenza vaccines used in DoD populations to prevent influenza acquisition. The vaccines are listed below:

- Licensed cell culture-based influenza vaccine:
 - Flucelvax Quadrivalent (Seqirus) (15µg HA/strain)
- Licensed recombinant vaccines:
- Flublok Quadrivalent (Protein Sciences) (45µg HA/strain)
- Licensed egg-culture based influenza vaccines:
 - Fluarix Quadrivalent (GlaxoSmithKline) 15µg HA/strain OR
 - FluLaval Quadrivalent (ID Biomedical Corp. of Quebec) 15µg HA/strain OR
 - Afluria Quadrivalent (Seqirus) 15µg HA/strain

Randomization Process:

Eligible subjects at each site will be randomized to receive a single dose of cell culture-based vaccine versus recombinant vaccine versus one of three standard dose egg-based vaccines.

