- Demographics (source: patient-completed quiestionnaire)
 - ° age
 - sex
 - ° weight

- height
- ethnicity
- ° race
- DEERS status (active duty, retiree, beneficiary)
- Military rank (active duty only)
- Subject may opt-in for a same-day and post vaccination self-collected blood sample using a Mitra Device. If they opt-in, their first sample will be taken the same day as their vaccination and their second sample will be taken 14-30 days later. Subjects may be asked to provide an end of study mitra kit.

Immunogenicity substudy subjects only

Study Day -30-0

• Venipuncture blood draw (approximately 40 mL)

Study Day 21-35

• Venipuncture blood draw (approximately 40 mL)

Acute Influenza-like Illness Surveillance

The main study will rely on the identification/ascertainment of individuals with acute ILI. During the ILI surveillance period, subjects will receive an automated email or text message (via REDCap platform) at 1 week intervals asking them if they have experienced ILI in the preceding 7 days. Subjects will get a reminder email or text 72 hours later and again 24 hours later if they have not responded to the weekly ILI surveillance. Influenza-like Illness (ILI) will be defined as:

- Cough OR sore throat AND
- Feverish/Chills OR Body aches/fatigue

The email or text messages (sent on a weekly basis) will also remind subjects to contact their medical provider should they experience any of the emergency signs described on the CDC's influenza website (https://www.cdc.gov/h1n1flu/homecare/warningsigns.htm, (Kellerman AL et al. Webbased self-triage of influenza-like illness during the 2009 H1N1 influenza pandemic. Ann Emerg Med. 2010 Sep;56(3):288-294). They are:

- Difficulty breathing or shortness of breath
- Pain or pressure in the chest or abdomen
- Sudden dizziness
- Confusion
- Severe or persistent vomiting (vomiting that goes on)
- · Flu-like symptoms that improve but then return with fever and worse cough

Collection of ILI symptom presence and severity data for a sequential 7-day period using the FLUPRO questionnaire

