Email or text messages responses from subjects who report symptoms meeting the ILI case definition will trigger an email or text message to a study coordinator, who will then contact the subject to schedule a virtual acute ILI visit. Subjects who respond to the email/text message stating that they are experiencing ILI symptoms will be sent a web link to a 7-day ILI severity questionnaire that will record the severity of ILI symptoms that they experienced in the past 24-72 hours in the online questionnaire. They will also receive daily email/text reminders to enter the symptom severity information for the past 24 hours for each of the remaining six days.

ILI surveillance in military trainees/recruits

Internet/email/text message access is not available to military recruits/trainees, and therefore they will not complete the FLUPRO questionnaire should they develop ILI symptoms. As such, at enrollment they will be guided to report to sick call should they develop acute ILI symptoms during the study follow-up period. Study coordinators will be on hand at the appropriate medical clinic to obtain acute ILI Visit Day 1 data and specimen collection. A convalescent ILI visit is not required for military recruits /trainees. **ILI Visits have the option of taking place virtually or in-person**

VIRTUAL ILI VISIT PROCEDURES

Acute ILI Visit #1 : visit during an acute phase of ILI episode

Subjects who develop ILI symptoms will undergo the following procedures:

- Self-collected nasal swab specimen.
- Self-collected blood sample (40 µL)
- ILI History
- If hospitalized:
 - ILI hospitalization status
 - Number of days hospitalized (if hospitalized for care)
- Number of work/duty days absent related to ILI episode

Visit #2- Convalescent Visit (21-35 post trigger): visit during convalescent phase of ILI episode Subjects who develop ILI symptoms will undergo the following procedures:

- Self- collected blood sample (40 µL)
- If hospitalized
 - ILI hospitalization status
 - Number of days hospitalized (if hospitalized for care)
- Total number of work/duty days absent related to ILI episode

IN-PERSON VISIT PROCEDURES

Visit #1- Acute ILI Visit

Subjects who develop ILI symptoms will undergo the following procedures:

- Self-collected nasal swab specimen.
- CRC collected nasal swab specimen
- In-clinic self-collected blood sample (40 µL) or intravenous blood draw (16 mL) (subject's choice)
- ILI History
- If hospitalized
 - ILI hospitalization status

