3.0 Methods

3.1 Main trial

This study will be a multi-center, pragmatic, prospective, non-blinded randomized controlled trial to assess the relative effectiveness of the licensed egg-based inactivated influenza vaccine to two other licensed vaccines, the cell-culture-based inactivated influenza vaccine and the recombinant influenza vaccine, in the prevention of laboratory-confirmed influenza infection in active duty members, military retirees and beneficiaries over four consecutive influenza seasons. Subject recruitment will take place at military treatment facilities.

Subjects will be active duty service members or other adults at least 18 years of age who are DEERS-eligible for care in the military treatment facility.

A total of 18,000 eligible subjects will be randomly allocated in a 1:1:1 ratio by study investigative team staff to one of the following groups:

- Group 1: Cell-culture-based (FlucelvaxR) influenza vaccine (~6,000 subjects)
- Group 2: Recombinant HA (FluBlokR) influenza vaccine (~6,000 subjects)
- Group 3: Egg-based influenza vaccines (~6,000 subjects)

Vaccine type will be known to the study investigative team and the participant.

Study Period

All participants who are not Marine Corps recruits will undergo surveillance for ILI during the influenza season (from October 2018-May 2019, September 2019-May 2020, September 2020-May 2021, and September 2021-May 2022).

Process

[figure not shown]

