During the influenza season, automated weekly email or text messages will be sent to subjects asking them if they have experienced ILI symptoms in the past 7 days. Subjects who meet the ILI case definition will be asked to complete an online 7-day symptom severity questionnaire and to schedule an acute ILI visit with a study coordinator. The questionnaire takes approximately 10 minutes to complete. At the acute ILI visit (Visit 1), study coordinators will record subjects' vital signs, ILI history, information on prescribed medications, hospitalization status, and work absences. They will also collect a nasal swab for diagnostic purposes and a blood sample for serologic studies and immune function. Subjects will contribute another blood specimen at a convalescent ILI visit approximately 28 days after the acute ILI visit (Visit 2). Information on ILI duration, hospitalization status, concomitant medications and work absences will be updated at this visit. Subjects will be monitored through as many ILI episodes as they experience, though subjects will only be compensated for the first 3 episodes. ILI episodes must be separated by at least 30 days. Information on ILI health care utilization and cost will be abstracted from the Military Health System Data Repository database by IDCRP study staff at the end of each influenza season.

Due to their lack of access to technology, participants who are Marine Corps recruits will not participate in the weekly surveillance; they will present when ill at the health clinic and nasopharyngeal and blood samples will be collected during Visit 1. Recruits are not required to schedule a Visit 2.

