3.2 Immunogenicity Sub-Study

Nested within this trial is an immunogenicity sub-study, in which 1,000 subjects will have their blood drawn prior to influenza vaccination and again at 21-35 days post-vaccination to assess changes in immune responses to the vaccines. Collection of a buccal swab for host genomic studies will be optional at enrollment or the 21-35 days post-vaccination visit.

	Recruits	Non-recruits	Non-recruits; Sub-Study
Consent and sociodemographic data collection	X	Х	Х
Sub-Study blood draw (pre-vaccination)			X
Vaccination with one of 3 vaccines	X	Х	Х
Weekly surveillance begins for non-recruits 14 days after vaccination		X	X
Sub-Study blood draw (post-vaccination)			X
ILIs - Visit 1 (if ILI is experienced) - nasopharyngeal swab, blood sample	X	X	X
ILI severity survey (if ILI is experienced)		Х	X
ILIs - Visit 2 (if ILI is experienced) - blood sample ~28d after Visit 1		X	X

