5.1.2 Relative Vaccine Effectiveness Estimate

Relative vaccine effectiveness (RVE) of cell-culture-based (FlucelvaxR) influenza vaccine as compared to egg-based influenza vaccines will be calculated using the following formula:

$$RVE_{cell} = \left(\frac{R_{egg} - R_{cell}}{R_{egg}}\right) X100\% = \left(1 - \frac{R_{cell}}{R_{egg}}\right) X100\%$$

Where:

 R_{cell} =incidence rate among the cell-culture-based influenza vaccination group R_{egg} =incidence rate among the egg-based influenza vaccination group

and

Relative vaccine effectiveness of recombinant HA (FluBlokR) influenza vaccines as compared to egg-based influenza vaccine will be calculated using the following formula:

$$RVE_{recombinant} = \left(\frac{R_{egg} - R_{recombinant}}{R_{egg}}\right) X100\% = \left(1 - \frac{R_{recombinant}}{R_{egg}}\right) X100\%$$

Where:

 $R_{recombinant}$ =incidence rate among the recombinant HA influenza vaccination group R_{egg} =incidence rate among the egg-based influenza vaccination group

The incidence rate equals the number of laboratory-confirmed influenza (definition 3.1.1) divided by the number of vaccinated individuals in each vaccination group.

The formula for the incidence rate will be:

 $Incidence Rate = \frac{Number of cases}{Number of vaccinated}$

Confidence intervals (95%) will be calculated using the standard formulas for relative risk. The upper and lower confidence intervals for relative vaccine effectiveness will be one minus the upper and lower calculated confidence intervals for the relative risk. The efficacy will be statistically significant if the calculated relative risk has a p-value of less than or equal to 0.025 (one-sided test). The interim analysis for relative effectiveness after the first influenza season uses a stricter p-value (<0.0001). Because of this, the final analysis will not need to adjust the p-value out of concerns about multiple looks.

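### Influenza surveillance starts at 4 weeks in the protocol and 14 days in the SAP, recruits have no stated start, and the primary endpoint has no onset window after vaccination

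*Protocol*

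**What the plan says.** **Non-recruits.** Protocol 9.5 has surveillance "beginning 4 weeks post-vaccination and ending when nationwide influezna activity has returned to baseline". The schedule table in SAP 3.2 reads "Weekly surveillance begins for non-recruits 14 days after vaccination". The text of SAP 3.1 ties surveillance to the calendar alone: "All participants who are not Marine Corps recruits will undergo surveillance for ILI during the influenza season", followed by month ranges and no offset from vaccination. Under Protocol 10.1 the survey goes out "at 1 week intervals asking them if they have experienced ILI in the preceding 7 days", so each message looks back a week.

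**Recruits.** They receive no weekly survey. Protocol 10.1 says that "at enrollment they will be guided to report to sick call should they develop acute ILI symptoms during the study follow-up period". SAP 3.1 says "they will present when ill at the health clinic and nasopharyngeal and blood samples will be collected during Visit 1". Neither gives a start day, and the follow-up period is not defined.

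**Endpoint and attack rate.** SAP 4.1.1 counts any RT-PCR-positive swab taken at presentation with ILI. SAP 5.1.2 states: "The incidence rate equals the number of laboratory-confirmed influenza (definition 3.1.1) divided by the number of vaccinated individuals in each vaccination group" (the cross-reference evidently means 4.1.1). Protocol 11.1 divides by the number enrolled. None of these sets a minimum time since vaccination. SAP 4.2 lists time since vaccination only as a possible subgroup.

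**The concern.** The trial compares how well three vaccines protect. An influenza illness that begins before any of them can have acted carries no information on that contrast, and counting it pulls the relative risk towards 1. Protocol 9.1 has enrolment running to December in the first season and to January in the others, so the weeks just after vaccination can overlap influenza activity.

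As written, the plan does not say which early illnesses count, and the answer may differ between recruits and everyone else. Two analysts working from these documents could build different numerators. SAP 3.1 states that vaccine type is known to the study team and the participant, so a window chosen later would be chosen with arm known.

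There is little power to spare. Protocol 11.1 reports 172 cases among 10,771 subjects over three seasons (1.6%) and says power has been too low.

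**Working it through.** **1. The plan's own figure.** Protocol 11.5 gives 2.3% against 1.54%, one-sided alpha 0.025, power 0.80, 15% loss to follow-up and 6,000 per arm. With pooled variance under the null and no continuity correction:

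n = [1.960·√(2p̄(1−p̄)) + 0.842·√(p₁(1−p₁)+p₂(1−p₂))]² / (p₁−p₂)², where p₁ = 0.023, p₂ = 0.0154 and p̄ = 0.0192.

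This gives 5,117 per arm, and 5,117/0.85 = 6,020, so the stated 6,000 reproduces. With 6,000 × 0.85 = 5,100 evaluable per arm, power is 79.9%.

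**2. Width and position of the gap for non-recruits.** The two stated starts differ by 28 − 14 = 14 days, or two weekly surveys. The 7-day look-back decides where the gap falls:

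| First message sent | SAP captures onset from | Protocol captures onset from | Disputed days |
|---|---|---|---|
| On the start day | about day 7 | about day 21 | about 7–20 |
| One week after the start day | about day 14 | about day 28 | about 14–27 |

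The documents do not say which applies. In the first row, non-recruit onsets in about days 7–13 also enter the numerator. In both rows, onset from day 14 is covered under the SAP start, and onset from day 28 is covered under either start.

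**3. Cases lost by starting 14 days later.** Assume uniform incidence over T days at risk, and multiply both attack rates by (1 − 14/T) with 5,100 per arm.
- T = 240: 14/240 = 5.8% of cases lost, power 77.4%.
- T = 120: 14/120 = 11.7% of cases lost, power 74.7%.

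The cost is 79.9 − 77.4 = 2.5 to 79.9 − 74.7 = 5.2 points.

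**4. Dilution by early cases in recruits.** Suppose a fraction f of egg-arm cases arises before protection, with relative risk 1 there and 0.67 afterwards. Then the observed relative effectiveness is 33% × (1 − f). If only recruits contribute, f = (recruits' share of cases) × (early share within recruits). The documents give neither input, so these values are assumptions:

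| Recruit share | Early share | f | Relative effectiveness | Power |
|---|---|---|---|---|
| 5% | 10% | 0.5% | 32.8% | 79.3% |
| 10% | 25% | 2.5% | 32.2% | 77.5% |
| 25% | 22% | 5.5% | 31.2% | – |
| 25% | 25% | 6.25% | 30.9% | 74.0% |

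The 22% is the top of an illustrative model: a bell-shaped season (SD 35 days) peaking late December to early February, enrolment September to January, and a group followed from day 0 for 60–90 days. Days 0–13 then hold about 5–22% of that group's cases.

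**5. Interaction with SAP 5.1.5.** Its sensitivity analysis keeps non-recruits with at least 50% or 75% of weekly survey data. The number of surveys due changes by two with the start date, so that set is not fully defined either.

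**The case against.** The strongest reply is that none of this biases one arm against another. The start of capture does not depend on arm, and allocation follows a randomised roster at each site. Dilution runs towards no difference and cannot by itself create a false claim of superiority. Counting every case after vaccination is also a defensible choice for a pragmatic trial. All of that stands. It limits the severity, but it does not tell the analyst which cases to count.

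SAP 5.1.5 also removes every recruit in a sensitivity analysis, which partly answers the concern. It sets no onset window, however, and leaves the primary analysis unchanged.

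Several stronger readings are tempting but are not supported:
- **Recruits are under capture from enrolment.** The instruction is given at enrolment, but it applies during a follow-up period whose start is undefined.
- **Early cases can count in recruits only.** The look-back may reach about day 7 in non-recruits, and SAP 3.1 gives no offset. Protocol 9.1 and 10.2 also bring in medical encounters and influenza test results, without saying whether these are endpoint cases.
- **Days 15–28 are treated as observed and case-free.** The measure is cases divided by people, with no person-time, so no days are credited as observed. A later start lowers the case count in every arm alike and leaves the relative risk unbiased if it is constant over time.
- **Dilution of 10–20% across all cases, giving 29.7% or 26.4%.** With 22% of recruit cases early, f = 10% needs recruits to supply 10/22 = 45% of all cases, and f = 20% needs 20/22 = 91%.

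**Conclusion.** The textual point is firm. There are two different stated starts for non-recruits, a third passage with no offset, no start day for recruits, and a primary numerator without an onset window. Recruits and non-recruits therefore contribute different risk windows to the same attack rate.

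The size is modest and rests on assumptions. The recruit contribution lowers the design relative effectiveness of 33% to about 31–33%. A day-28 start costs about 2.5 to 5 points of power relative to day 14. The first range leaves out any early non-recruit cases admitted by the look-back, which would add to the dilution and cannot be sized from the documents.

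The effect is the same in every arm, so this is not confounding. Severity is moderate: worth settling before analysis because it determines which cases enter an unblinded primary comparison, but not a threat to the validity of the randomised contrast.

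**What to change.** 1. Reconcile Protocol 9.5, SAP 3.1 and the SAP 3.2 table. Record in the SAP the surveillance start actually operated in each season and the period covered by the first survey.
2. Add to SAP 4.1.1 and 5.1.2 one case-counting window applied alike to recruits and non-recruits: ILI onset at least 14 days after vaccination. This is the SAP's own surveillance start. The documents offer no immunological basis for it, so the SAP should state its reason.
3. Prespecify an analysis with onset at least 28 days after vaccination, the window covered under both rules. Make it primary if the protocol's 4-week start was the one operated. A 14-day window would then still count recruit cases from a period in which non-recruits were not fully surveyed.
4. In SAP 5.1.5, define the number of surveys due from the reconciled start.

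The cost is SAP wording and a short protocol clarification. Vaccination is a study visit and onset date is already recorded at the acute ILI visit (Protocol 10.2). The downside is that a few early cases leave the numerator, and more do so if the 28-day window becomes primary.
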